12.0 AUDITING

Since Washington University is the coordinating center, each site will be audited annually by Siteman Cancer Center personnel (QASMC) unless the outside institution has an auditing mechanism in place and can provide a report. The outside sites will be asked to send copies of all audit materials, including source documentation. The audit notification will be sent to the Washington University Research Patient Coordinator, who will obtain the audit materials from the participating institution.

Notification of an upcoming audit will be sent to the research team one month ahead of the audit. Once accrual numbers are confirmed, and approximately 30 days prior to the audit, a list of the cases selected for review (up to 10 for each site) will be sent to the research team. However, if during the audit the need arises to review cases not initially selected, the research team will be asked to provide the additional charts within two working days.

Additional details regarding the Auditing Policies and Procedures can be found at <https://siteman.wustl.edu/wp-content/uploads/2015/QASMC-Policies-and-Procedures-03.31.2015.pdf>

13.0 MULTICENTER REGULATORY REQUIREMENTS

Washington University requires that each participating site sends its informed consent document to be reviewed and approved by the Washington University Regulatory Coordinator (or designee) prior to IRB/IEC submission.

Site activation is defined as when the secondary site has received official written documentation from the coordinating center that the site has been approved to begin enrollment. At a minimum, each participating institution must have the following documents on file at Washington University prior to study activation:

- Documentation of IRB approval of the study in the form of a letter or other official document from the participating institution's IRB. This documentation must show which version of the protocol was approved by the IRB.
- Documentation of IRB approval of an informed consent form. The consent must include a statement that data will be shared with Washington University, including the Quality Assurance and Safety Monitoring Committee (QASMC), the DSMC (if applicable), and the Washington University study team.
- Documentation of FWA, signed FDA Form 1572 (if applicable), and the CVs of all participating investigators.
- Protocol signature page signed and dated by the investigator at each participating site.

The coordinating center Principal Investigator (or designee) is responsible for disseminating to the participating sites all study updates, amendments, reportable adverse events, etc. Protocol/consent modifications and IB updates will be forwarded electronically to the secondary sites within 4 weeks of obtaining Washington University IRB approval. Activated secondary sites are expected to submit protocol/consent/IB modifications to their local IRBs within 4 weeks of receipt unless otherwise noted. Upon the secondary sites obtaining local IRB approval, documentation of such shall be sent to the Washington University study team within 2 weeks of receipt of approval.

Documentation of participating sites' IRB approval of annual continuing reviews, protocol amendments or revisions, all SAE reports, and all protocol violations/deviations/exceptions must be kept on file at Washington University.

The investigator or a designee from each institution must participate in a regular conference call to update and inform regarding the progress of the trial.

14.0 STATISTICAL ANALYSIS METHODS AND SAMPLE SIZE

14.1 Analysis Populations

Intent-to-Treat - The intent-to-treat (ITT) population will be defined as all patients who receive at least one dose of decitabine.

Efficacy-Evaluable - The efficacy-evaluable (EE) population will be defined as all patients who receive at least one cycle of treatment.

Safety - The safety population will be defined as all patients with at least one dose of decitabine.

14.2 Statistical Analysis

14.2.1 Descriptive Analyses

Patient Disposition: The number of patients discontinued, the reasons for discontinuation, and the number of cycles administered will be summarized.

Demographics and Baseline Characteristics: Descriptive summary statistics will be provided for demographic and important baseline characteristics. For continuous variables, the number of patients, mean, standard deviation, median, minimum and maximum will be provided. For categorical variables, the number and percent of patients in each demographic/characteristic category will be summarized.

14.2.2 Primary Endpoint Analysis

The primary end-point of this phase II study is the correlation biomarkers with overall response in AML/MDS patients to decitabine.

We will correlate the presence of patient specific mutations (especially mutations in *DNMT3A*, *IDH1*, *IDH2*, and *TET2*) with overall response rates. Mutation rates in these genes and in other patient-specific genes will be correlated with overall response and their respective 95% confidence intervals will be provided.

Statistical considerations. The relationship between AML/MDS-associated mutations and the responsiveness to decitabine will be described by contingency tables and assessed using Chi-square test or Fisher's exact test as appropriate. The differentially expressed genes between responders and non-responders will be determined using the significance analysis of microarray (SAM). Multivariate logistic regression will also be fit to adjust the potential confounding effects of other demographic and clinical characteristics. The resultant critical *P* values will be corrected for multiple testing. Since the Bonferroni correction is known to be too conservative, a permutation analysis (e.g., 10,000 random assignments for

responsive status) will be used to derive an empirical critical *P* value. The new critical p-value is the number of permutation tests which yield a lower p-value than the original test divided by the total number of permutation tests.[61]

A power analysis was performed using Chi-square test for the association between mutation and response to decitabine. The frequency of *DNMT3A*, *IDH1/2*, and *TET2* mutations in AML and MDS patients are each between 15% and 30% in multiple cohorts.[29-37] **Table 3** shows the minimal detectable differences of response rates between mutant and wild-type cases, assuming an expected overall 45% CR/CRi rate and 80% power. For an average of 20% frequency of a mutated gene, for example, 100 patients will provide 80% power to detect 30% difference at a 2-sided 0.1 alpha error. The purpose of this study is to determine whether any of these mutations result in a clinically significant association that would warrant pre-treatment testing. We believe that a reasonable cut off would be if at least 30% of clinical response could be attributed to the presence of a specific mutation. However, we anticipate that more power could be achieved as we assess patient groups with combined characteristics (e.g. *DNMT3A* mutation or loss of *DNMT3A* expression). In addition, we expect that the majority of the enrolled 125

Table 3. Detectable mutation associated response rates (80% power, $\alpha = 0.05$)

Total N	% of patients with a given mutation	Detectable response difference	Sensitivity of mutation to predict response at minimum detectable response difference*
100	15%	0.40	80%
	20%	0.35	75%
	30%	0.30	67%
	40%	0.27	61%
	50%	0.26	58%

* Assuming the overall response rate (CR/CRi) of 45%

patients can be used in the analysis (since all of our molecular information will be acquired within 30 days of enrollment, we anticipate a drop-out rate of 20% or less).

14.2.3 Secondary Endpoint Analyses

The overall response rate (CR/CRi/PR) and complete response rate (CR/CRi) will be compared with historical controls[2], and the 95% confidence intervals will be provided.

The rate of patient specific mutation clearance after 10, 28, and 56 days of therapy will be determined using an Illumina based platform. We will compare the rate of mutation clearance between the patients who achieve a CR/CRi after 4 cycles and those who do not. We anticipate that we will identify between 6 and 25 exonic SNVs per case (the range obtained with >200 AML samples sequenced to date with whole genome or exome sequencing), and that the expected 95% confidence interval of the mean variant allele frequency will be $\pm 2.56\%$ and $\pm 1.25\%$,

respectively, if we assume an anticipated standard deviation of 3.2% within the same clone. The change of tumor burden over time and its association with clinical response will be assessed using 2-way ANOVA for repeated measurement data, followed by the ad-hoc multiple comparisons for between-group differences (e.g., responders vs. non-responders) at given time points as well as the between-time differences within each group. The resultant critical P values will also be corrected using permutation analysis for multiple testing.

The percent decrease in bone marrow methylcytosine will be calculated on day 10 ± 1 . We will compare this reduction with previously published data and between the patients who achieve CR/CRi and those who do not. The correlation of peak plasma levels of decitabine with response will be assessed using 2-sample t-test or Mann-Whitney non-parametric rank-sum test as appropriate. The change of total bone marrow DNA methylcytosine from baseline and its association with both steady-state plasma drug levels and response will be assessed using 2-way ANOVA for repeated measurement data, followed by the ad-hoc multiple comparisons for between-group differences (e.g., responders vs. non-responders) and between-time differences. Similar analyses will be performed for the correlation of expression profiles and SNP analysis with pharmacokinetic data.

Statistical power justification. A power analysis was performed using two-sample t-test for between-group difference and paired t-test for the change over time. For tumor clearance, this will provide $> 99\%$ power to detect a 10% difference in the means at two separate time points for clones with 6 or more variants, and $> 98\%$ power to detect a 15% difference if there are 3 or more variants per clone with $\alpha = 0.05$ (power will decrease to 91% and 82%, respectively, in cases where the standard deviation is 4.7%, the maximum we have observed thus far). For pharmacologic correlations, we anticipate 85% power to determine a 25 ng/ml difference between the average C_{\max} of 45 evaluable responders and 55 evaluable non-responders with an anticipated average C_{\max} of 70 ng/ml and a standard deviation of 40 ng/ml within the entire cohort, and with $\alpha = 0.05$. [22] We believe a less significant difference would not be sufficient to warrant application in clinical decision making (i.e. whether to continue therapy for more than 1 cycle). We anticipate 99% power to determine a difference of 20% in the reduction of bone marrow methylcytosine between 45 evaluable responders and 55 evaluable non-responders with an expected standard deviation of 15% and $\alpha = 0.05$. [28, 66-68] The difference in methylcytosine reduction previously observed was 30% between patients achieving CR/PR and those with only hematologic improvement. [28]

Time to relapse and time to death will also be listed for each patient.

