We and others have recently used whole genome sequencing to identify recurrent, somatic mutations in AML and MDS patients in four genes that are involved in methylcytosine regulation: *DNMT3A*, *IDH1*, *IDH2*, and *TET2*.^[29-37] Collectively, nearly half of all AML/MDS patients have a mutation in one of these four genes. *DNMT3A* mutations are associated with an adverse outcome in AML patients treated with cytotoxic chemotherapy.^[35, 38] However, it is not yet clear whether the presence of mutations in one or more of these genes is associated with response or resistance to decitabine.

In this study, we will treat patients with the current state-of-the-art decitabine schedule.^[3] We will perform exome sequencing on all patients and correlate response with mutation status, rate of mutation clearance, expression profile, plasma decitabine levels, and DNA

methylcytosine content reduction. This approach will comprehensively assess genomic and pharmacologic parameters that could clinically predict patient response to decitabine.

In this study, we will combine analysis of patients with AML and MDS. Recent genomic analysis has shown that AML and MDS have shared mutations in many of the same genes, shared patterns of mutation acquisition, and shared patterns of mutation evolution.[39, 40] Furthermore, MDS, like AML, presents with clonal hematopoiesis, even when the morphologic blast count is zero.[36] Because this study will identify and track the rate of clearance of patient specific mutations, and because decitabine has been shown to have efficacy in both AML and MDS patients, [2, 3, 16-19, 41-45] combining analysis of AML and MDS patients is reasonable. Asymptomatic MDS patients are excluded because these patients are typically followed with watchful-waiting rather than with chemotherapy.

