Because all patient-specific exome-discovered mutations will be assessed a second time in the primary bone marrow sample as well as the Cycle 1 Day 10 \pm 1, Cycle 1 Day 28 \pm 4, and Cycle 2 Day 28 \pm 4 bone marrow samples, this study will also serve to validate all exome-discovered mutations. This is important, because exome sequencing is associated with a 20-50% false-discovery rate depending on type I error tolerated (mutation-calling algorithms are typically set for greater sensitivity than specificity). Thus, many mutations discovered during exome sequencing are incorrect. This second analysis of these mutations will serve to exclude these false positive calls.

3. To correlate the bone marrow expression profile from pre-study and Cycle 1 Day 10 \pm 1 with response to decitabine.

We will correlate expression signatures, and changes in expression signatures, with:

- Achievement of clinical CR,
- Mutation status.

4. To correlate the extent of bone marrow DNA hypomethylation on Cycle 1 Day 10 \pm 1 with response to decitabine.

We will assess the percent reduction in bone marrow methylcytosine content using LC-MS. Patients will be evaluated pre-study and Cycle 1 Day 10 \pm 1. The change in DNA methylcytosine content will be correlated to:

- Achievement of clinical CR,
- Change in expression signature.

This will determine whether inadequate blast exposure to decitabine correlates with drug resistance.

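### The Day-10 methylcytosine comparison has no mutation term, so it can show that the fall predicts response but cannot separate low drug exposure from a mutation effect

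*Combined protocol and SAP*

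**What the plan says.** The combined file holds several protocol versions; the text relevant here is the same in all of them.

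- **Analysis (14.2.3).** "The percent decrease in bone marrow methylcytosine will be calculated on day 10" (with a one-day window), and then "We will compare this reduction with previously published data and between the patients who achieve CR/CRi and those who do not". The change from baseline, and its association with plasma level and response, "will be assessed using 2-way ANOVA for repeated measurement data". No covariate is named.
- **Power (14.2.3).** "We anticipate 99% power to determine a difference of 20% in the reduction of bone marrow methylcytosine". The calculation assumes 45 patients with a response and 55 without, an SD of 15 points and alpha 0.05. The test behind this is an unadjusted two-sample t-test.
- **Genes (1.1 and 14.2.2).** DNMT3A, IDH1, IDH2 and TET2 are introduced as "four genes that are involved in methylcytosine regulation". The primary analysis singles out the same genes as candidate predictors of response.
- **Interpretation (1.3, methylcytosine item).** "This will determine whether inadequate blast exposure to decitabine correlates with drug resistance".
- **Links to mutation status (1.3).** The clearance item and the expression item are both to be correlated with mutation status. The methylcytosine item is correlated only with CR and with change in expression signature.
- **Adjustment elsewhere.** The logistic model in 14.2.2 sits under the primary endpoint and names demographic and clinical characteristics, not molecular ones. The four-gene subgroup in 14.2.5 applies to the primary and overall survival endpoints.

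**The concern.** On the protocol's own account, mutation status may affect both the methylcytosine fall and response. If it does, responders and non-responders differ in their share of carriers. Part of any difference in the fall then reflects who carries the mutation and not how much drug reached the blasts. If carriers respond better and also show a larger fall, non-responders look under-exposed when they are not. If carriers show a smaller fall, a real exposure signal is masked.

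This matters because Section 1.3 gives the result an exposure meaning, and nothing else in the trial can check that meaning. Section 14.2.3 still refers to plasma levels, but only the last version in the file schedules a plasma sample. In the other versions the methylcytosine fall is the only stand-in for exposure.

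**Working it through.** **Inputs from the documents.** 45 responders and 55 non-responders; SD 15 points; alpha 0.05 (two-sided assumed, since sidedness is not stated); target difference 20 points; overall CR/CRi rate 45%; Table 3 rows of 50% frequency with difference 0.26, and 20% with 0.35. The 50% row is the closest to the statement in 1.1 that nearly half of patients carry one of the four mutations.

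**Assumption.** The documents give no figure for a mutation effect on the fall. A range of 5 to 20 points is used.

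**1. The plan's own power.** SE = 15 × √(1/45 + 1/55) = 15 × 0.201 = 3.02 points. The ratio 20/3.02 = 6.6 gives power above 99.9%, so the stated 99% is met. The difference detectable with 80% power is 3.02 × (1.960 + 0.842) = 8.4 points.

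**2. Carrier imbalance between response groups.**
- 50% row: carriers respond at 0.45 + 0.5 × 0.26 = 0.58, non-carriers at 0.45 − 0.5 × 0.26 = 0.32. The carrier share is 0.5 × 0.58/0.45 = 0.644 among responders and 0.5 × 0.42/0.55 = 0.382 among non-responders. Gap: 0.263.
- 20% row: response rates are 0.73 and 0.38. The carrier share is 0.2 × 0.73/0.45 = 0.324 against 0.2 × 0.27/0.55 = 0.098. Gap: 0.226.

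**3. Spurious difference, with no link between fall and response inside mutation groups.** Spurious difference = gap × mutation effect. The rejection rates below come from simulation with N = 100 and residual SD 15.

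| Assumed mutation effect (points) | Spurious difference, 50% row | Unadjusted test significant, 50% row | Spurious difference, 20% row | Unadjusted test significant, 20% row |
|---|---|---|---|---|
| 5 | 1.3 | about 7% | 1.1 | about 6–7% |
| 10 | 2.6 | about 13% | 2.3 | about 11% |
| 15 | 3.9 | about 21–23% | 3.4 | about 18% |
| 20 | 5.3 | about 31% | 4.5 | about 26% |

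With a mutation term in the model, the rejection rate returns to about 5% throughout.

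**4. Upper limit.** A spurious difference of 20 points would need a mutation effect of 20/0.263 = 76 points (50% row) or 20/0.226 = 88 points (20% row).

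**5. Opposite directions.** If half the carriers shift up and half down by the same amount, with equal effects on response, the unadjusted test rejects about 5% of the time. The inflation disappears.

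**6. Power after adjustment.** Take four gene terms plus baseline (93 degrees of freedom) and let these covariates explain 30% of the variation in response status. SE = 3.02/√0.70 = 3.60, the ratio is 20/3.60 = 5.5, and power is 0.9998.

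**The case against.** **The objective is predictive.** Section 2.2 asks whether biomarkers correlate with response, and Section 1.3 also speaks of correlation. For that question the unadjusted comparison is the right one. This stands. A reader might infer that the planned analysis is invalid, or that the trial would declare low exposure to be the cause of resistance; the documents say neither. What remains is that the sentence in 1.3 equates a small fall with inadequate exposure, and the planned comparison cannot support that step alone.

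**The key input is assumed.** The genes are said to be involved in methylcytosine regulation, but no size or direction is given, and 1.1 says their relation to response is not yet clear. If either link is absent, there is no confounding. The current inclusion criteria require adverse-risk karyotype or TP53 mutation, so the carrier frequency may also differ from the general figure. All of this stands, and is why the result is a range.

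**Baseline.** A reader might also infer that leaving baseline methylcytosine out as a covariate creates an artefact. The documents do not support that. Baseline is already the denominator of the percent decrease and a time point in the ANOVA. Suppose responders start 10% higher and both groups reach 70% of the non-responder baseline. The falls are 1 − 0.70/1.10 = 36.4% and 30%, but the responders did lose more. The groups are not randomised, so change scores and baseline-adjusted models answer different questions and neither is automatically correct.

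**Adjustment can remove signal.** If a mutation acts on response through methylcytosine, the adjusted result omits that part. In one illustration (a 20-point mutation effect on the fall, with response depending only on the fall, logit slope 0.03, all assumed), power dropped from 73% to 58%. This is a reason to report both results, not to replace one with the other.

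**Conclusion.** The point holds as a cheap improvement. The planned comparison answers whether the Day-10 fall predicts response, but cannot distinguish low exposure from an effect of the genes that the trial itself tests as predictors. Under Table 3's 50% row and an assumed mutation effect of 5 to 20 points acting in one direction, the spurious difference is about 1.3 to 5.3 points, significant in about 7% to 31% of trials against a nominal 5%. It does not threaten a finding near the planned 20 points. It matters for smaller differences, down to and below the 8.4 points that the trial can detect with 80% power. The size rests on the assumed mutation effect, on a shared direction across genes, and on mutation frequencies that may not match the enrolled population.

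**What to change.** 1. Keep the unadjusted comparison in 14.2.3 as planned.
2. Add one pre-specified linear model of the Day-10 methylcytosine fall on CR/CRi status, with four-gene mutation status as covariate: a single any-of-four indicator, or separate genes if numbers allow. Baseline methylcytosine can be an optional sensitivity covariate.
3. In 1.3, add mutation status to the correlates of the methylcytosine item, as is already done for the clearance and expression items.
4. Report the unadjusted and adjusted results side by side, and state the exposure reading only where the adjusted result is shown.

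**Cost.** A few lines of text and one extra model on data already collected. It uses a few degrees of freedom and loses some power if mutation acts through methylcytosine. Power for the planned 20-point difference stays above 99%.

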14.2.4 Safety Analysis

Extent of Exposure – Duration (number of cycles/infusions) of decitabine doses (cumulative and intensity) will be summarized.

Adverse Events - All adverse events will be coded using NCI CTCAE v. 4.0. The incidence of treatment-emergent adverse events (number and percent of patients reporting the adverse event at least once during the study) will be summarized. In addition, adverse events will be summarized by investigator attribution of relationship to study medication and by grade. Similar summaries will be provided by treatment cycle.

Clinical Laboratory Evaluation – Applicable laboratory parameters will be graded according to NCI CTCAE version 4.0. The incidence of maximum grade (number and percent of patients experiencing the maximum grade during the study) will be summarized for each laboratory parameter. Similar summaries will be provided by treatment cycle. Graphical displays of select hematological parameters will also be provided.

Vital Signs, Physical Findings, and Other Safety Observations – Vital signs, findings from physical examinations, ECOG scores and weights will be presented in listing format.

